2.3.1.1. Other Clinically Relevant Information

Additional details concerning safety observations from clinical studies and for which a causal association has not been established or which are of minimal clinical significance may be found in the Investigator's Brochures (GlaxoSmithKline Document Number [RH2009/00003/06](#) [CAB IB], [RPV IB](#), 2017).

Adverse Events of Special Interest:

Seizure

Three cases of seizures have occurred in the cabotegravir programme cumulatively through 15 May 2016. Two of the cases occurred in HIV uninfected subjects with a prior history of seizure and one case involved a subject in study 200056 with circumstantial and anecdotal evidence of illicit drug use. Overall, there is not convincing evidence that cabotegravir exposure may be causally associated with seizure or with reduction of seizure threshold, due to the low frequency of reports, the confounders present in the cases received to date and lack of any pre-clinical signal or identified plausible mechanism. However, seizure and seizure-like events are considered as AEs of special interest for close monitoring in future studies. Subjects with an unstable or poorly controlled seizure disorder will be excluded from study participation. All cases of prior seizure history should be discussed with the Medical Monitor prior to enrolment.

2.3.2. Benefit Assessment

The antiviral activity against HIV-1 of CAB has been well established through Phase 2a and Phase 2b studies. RPV is an established antiviral agent against HIV-1 in treatment naive patients, with long term durability (>96 weeks in Phase 3 and >240 weeks in Phase Ib).

Participants receiving CAB LA + RPV LA are anticipated to benefit from maintenance of virological suppression using LA agents. Participants randomized to receive CAB LA+ RPV LA Q4W or Q8W weekly dosing will not need to take concomitant daily oral therapy. Adherence in these participants is expected to be improved and will be directly observed during IM injections. Efficacy of this two-drug regimen, as IM agents, has been demonstrated through Week 96 of the ongoing 200056 study. The reduction in ART, and the discontinuation of NRTIs, may offer long term safety and tolerability benefits in these participants.

2.3.3. Overall Benefit:Risk Conclusion

Taking into account the measures taken to minimize risk to participants participating in this study, the potential risks identified in association with CAB LA and RPV LA Q4W and Q8W regimens, and the study as a whole are justified by the anticipated benefits that may be afforded to treatment-experienced patients with HIV-1 infection.

3. OBJECTIVES AND ENDPOINTS

Objectives	Endpoints
Primary	
To demonstrate the non-inferior antiviral activity of CAB LA + RPV LA every 8 weeks (every two months) compared to CAB LA + RPV LA every 4 weeks (monthly) over 48 weeks in suppressed HIV-1 infected antiretroviral therapy (ART)-experienced participants	Proportion of participants with plasma HIV-RNA greater than or equal to 50 copies/mL as per Food and Drug Administration (FDA) Snapshot algorithm at Week 48 (Intent-to-Treat Exposed [ITT-E] population)
Secondary	
To demonstrate the antiviral and immunologic activity of CAB LA + RPV LA every 8 weeks compared to CAB LA + RPV LA every 4 weeks	
Proportion of participants with plasma HIV-1 RNA <50 c/mL (c/mL) at Week 24, Week 48 and Week 96 using the FDA Snapshot algorithm (Intent-to-Treat Exposed [ITT-E] population)
 
Proportion of participants with protocol-defined confirmed virologic failure (CVF) through Week 24, Week 48 and Week 96
 
Proportion of participants with HIV-RNA greater than or equal to 50 c/mL as per FDA Snapshot algorithm at Week 24, and Week 96
 
Absolute values and changes from Baseline in viral load and CD4+ cell counts over time including Week 48 and Week 96

To evaluate the safety and tolerability of CAB LA + RPV LA every 8 weeks compared to CAB LA + RPV LA every 4 weeks	
Incidence and severity of AEs and laboratory abnormalities over time including Week 24, Week 48 and Week 96
 
Proportion of participants who discontinue treatment due to AEs over time including Week 24, Week 48 and Week 96
 
Change from Baseline in laboratory parameters over time including Week 48 and Week 96

Objectives	Endpoints
To assess viral resistance in participants experiencing protocol-defined confirmed virologic failure	Incidence of treatment emergent genotypic and phenotypic resistance to CAB, RPV through Week 24, Week 48 and Week 96
To characterize CAB and RPV concentrations and population pharmacokinetics and identify important determinants of variability	
Plasma PK parameters for CAB LA and RPV LA (when evaluable, C_{trough}, concentrations post dose [$\sim C_{max}$], and area under the curve [AUC])
 
Demographic parameters including, but not limited to, age, sex, race, body weight, body mass index, and relevant laboratory parameters will be evaluated as potential predictors of inter- and intra-participant variability for pharmacokinetic parameters


To assess preference for CAB LA + RPV LA every 8 weeks or CAB LA + RPV LA every 4 weeks LA compared to oral antiretroviral (ARV)
 
To assess preference for CAB LA+ RPV LA every 8 weeks compared to CAB LA + RPV LA every 4 weeks
	Preference for CAB LA + RPV LA every 8 weeks or CAB LA + RPV LA every 4 weeks compared to oral ARV and preference for CAB LA + RPV LA every 8 weeks compared to CAB LA + RPV LA every 4 weeks will be assessed using a preference questionnaire at week 48 (or Withdrawal).
To assess patient reported health-related quality of life, treatment satisfaction, injection tolerability, and treatment acceptance.	
Change from Baseline (Day 1) in HRQoL at Week 24, and Week 48 (or Withdrawal)
 
Change from baseline (Day 1) in total “treatment satisfaction” score, and individual item scores of the HIV Treatment Satisfaction Status Questionnaire (HIVTSQs) at Week 24, and 48, (or Withdrawal)
 
Change in treatment satisfaction over time using the HIV Treatment Satisfaction Change Questionnaire HIVTSQc at Week 48 (or Withdrawal).
 
Change from Week 8 in Dimension scores (“Bother of ISRs”, “Leg movement”, “Sleep”, and “Injection Acceptance”) and individual item scores assessing pain during injection, anxiety before and after injection, willingness to be injected in the future and overall satisfaction with mode of

Objectives	Endpoints
	
administration over time will be assessed using the Perception of iNjection questionnaire (PIN) at Weeks 8, 24, and 48 (or Withdrawal)
 
Change from Baseline (Day 1) in treatment acceptance at Week 24 and Week 48 (or Withdrawal) will be assessed using the “General acceptance” dimension of the Chronic Treatment Acceptance (ACCEPT) questionnaire

Exploratory	

To evaluate the antiviral and immunologic effects, safety and tolerability, and viral resistance of CAB LA + RPV LA for all participants in the Extension Phase.
	
Proportion of participants with plasma HIV-1 RNA <50 c/mL over time
 
Proportion of participants with confirmed virologic failure over time
 
Incidence of treatment emergent genotypic and phenotypic resistance to CAB and RPV in over time
 
Incidence and severity of AEs and laboratory abnormalities over time
 
Proportion of participants who discontinue treatment due to AEs over time
 
Absolute values and changes in laboratory parameters over time
 
Incidence of disease progression (HIV-associated conditions, acquired immunodeficiency syndrome [AIDS] and death)

To explore the effect of patient characteristics on virologic and immunologic responses to CAB LA+ RPV LA every 8 weeks compared to CAB LA + RPV LA every 4 weeks
	
Proportion of participants by patient subgroup(s) (e.g., by age, gender, BMI, race, HIV-1 subtype, Baseline CD4+, type of oral treatment [NNRTI, PI, or INSTI], duration prior CAB LA and RPV LA exposure [0 weeks, 1-24 weeks, > 24 weeks]) with HIV-RNA greater than or equal to 50 c/mL, and with protocol-defined confirmed virologic failure over

Objectives	Endpoints
	
time including Week 48 and Week 96 using the Snapshot algorithm for the ITT-E population
 
Change from Baseline in CD4+ cell counts by subgroups at Week 48 and Week 96

To explore relationship(s) between plasma concentrations of CAB and RPV and pharmacodynamic endpoints.
	
Relationship between plasma CAB and RPV concentrations and virologic, immunologic responses, and/or occurrence of adverse events [AEs] over time.

To assess reason for switching using a single question.
 
To assess reason for continuation using a single question
	
For patients randomized from oral SOC, the reasons for willingness to switch ART at baseline (Day 1) will be assessed
 
For patients randomized from CAB LA + RPV LA every 4 weeks in ATLAS, the reasons for willingness to continue long-acting ART at baseline (Day 1) will be assessed

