The final dosing of current daily oral ART regimen should occur the day prior to randomization to avoid overlap of treatment regimens however, if the participant takes current ART prior to coming into the clinic, randomization and initiation of oral CAB and RPV should continue as planned for Day 1. At the Week 4a visit, safety assessments (including e.g., clinical chemistries) will be performed as per the Time and Events Table to determine individual safety and tolerability prior to the initial administration of CAB LA + RPV LA. Dosing of CAB LA + RPV LA Q4W or Q8W will initiate at the Week 4b visit once safety labs from Week 4a are available and have been reviewed.

Subjects receiving oral SOC treatment and randomized to Q4W injections will receive loading doses of CAB LA 600 mg + RPV LA 900 mg on **Week 4b** followed by maintenance injections of CAB LA 400 mg + RPV LA 600 mg every 4 weeks thereafter.

Subjects receiving oral SOC treatment and randomized to Q8W injections will receive doses of CAB LA 600 mg + RPV LA 900 mg on **Week 4b and Week 8** followed by identical maintenance dose injections every 8 weeks thereafter.

All injections should be planned as single injections per drug.

4.2.2.1.1. IM injections every 4 weeks (Q4W from SOC):

Week 4b visit only - CAB LA 600 mg + RPV LA 900 mg, each given as 1 X 3 mL IM injection

Week 8 visit and Q4W thereafter - CAB LA 400 mg IM + RPV LA 600 mg IM every 4 weeks for 100 weeks, each given as 1 X 2 mL IM injection

At Week 4b, participants will return to the clinic, take the last oral dose (CAB 30 mg + RPV 25 mg), and receive the first CAB LA (600 mg) + RPV LA (900 mg) injections (within 2 hours of the final oral dose of CAB + RPV). The first injections with IM CAB LA + RPV LA at Week 4b can be performed once central lab results are available and safety parameters are reviewed from the Week 4a visit.

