4.2.2.2. Participants transitioning from ATLAS and currently receiving CAB LA + RPV LA Q4W

Subjects receiving Q4W injections within ATLAS and randomized to receive Q4W injections in Study 207966 will continue receiving maintenance injections Q4W as scheduled and will not require a loading dose on Day 1.

Subjects receiving Q4W injections within ATLAS and randomized to receive Q8W injections in Study 207966 will receive doses of CAB LA 600 mg + RPV LA 900 mg on Day 1, one month after their last Q4W maintenance dose, in order to align with Day 1 of study randomization. Subjects will not require an intermediate dose at Week 4 and will receive their next Q8W maintenance injections at Week 8 and Q8W thereafter.

Participants transitioning from the ATLAS study and on CAB LA + RPV LA Q4W treatment will be randomized at Day 1 to either continue Q4W administration or transition to Q8W administration of CAB LA + RPV LA. The first injection visit for the ATLAS-2M study can be performed once the final central lab results from the ATLAS study are available and safety parameters have been reviewed. Screening labs determining eligibility for ATLAS-2M can be collected at Week 48 (at minimum) for participants originally randomized to the Q4W arm within ATLAS. Screening labs for participants who transitioned from SOC to Q4W injections within the ATLAS Extension Phase may be obtained at ATLAS Week 56b (following the CAB + RPV Oral lead-in period) or at subsequent ATLAS visits after receiving one set or a short course of Q4W injections. The transition from the final ATLAS to ATLAS-2M Day 1 dosing must occur 4 weeks (± 7 days) from the final injections received in ATLAS

Dosing for participants transitioning from CAB LA + RPV LA Q4W in ATLAS is as follows:

4.2.2.2.1. IM injections every 4 weeks (Q4W from ATLAS Q4W):

Starting at Day 1, all injections will continue with maintenance doses of CAB LA 400 mg and RPV LA 600 mg administered every 4 weeks (± 7 days). In addition, the time between injection visits will be limited to a maximum of 5 weeks. The Medical Monitor must be contacted if the length of time between injections exceeds or is projected to exceed 5 weeks.

4.2.2.2.2. IM injections every 8 weeks (Q8W from ATLAS Q4W):

Participants transitioning from ATLAS and randomized to receive CAB LA + RPV LA Q8W injections will initiate Q8W dosing at the Day 1 visit as follows:

Day 1- CAB LA 600 mg + RPV LA 900 mg IM, each given as 1 X 3 mL IM injection

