discontinuation rate due to AEs, including injection site reaction (ISR) related AEs in either dosing arm, with no significant dose-dependent trends in safety parameters. On the basis of 200056 Week 48, and Week 96 data, Q4W and Q8W IM dosing are being progressed into Phase 3 for further clinical development, respectively. The CAB LA + RPV LA Q4W regimen is currently under evaluation in the ongoing Phase III ATLAS study.

The open-label design best suits the objectives of this study. A double-dummy design could not be undertaken given the logistical challenges of blinding each regimen. Because 2 injections of each investigational product are administered at every visit, a double-dummy design would require all subjects to chronically receive 4 injections per Q4W visit (2 active and 2 placebo), which could be intolerable for patients. In addition, the volume of CAB LA and RPV LA injections will differ significantly between Q8W and Q4W IM injections (3 mL vs 2 mL each), it would not be logistically feasible to blind site staff nor patients from the study treatments being administered.

Participants randomized to receive CAB LA + RPV LA Q8W IM administration will be required to participate in clinic visits approximately every 8 weeks while participants randomized to receive Q4W IM administration will be required approximately monthly clinical visits. Importantly, secondary objectives of this study are to understand the acceptability, tolerability, and patient reported preferences to these novel injectable regimens. An unblinded study design supports collection of participant preference data in a way that would not be possible if a double-blind, double-dummy design were implemented. If the Q8W arm were required to receive blinded placebo injections every month, the value of comparing safety, tolerability, and convenience of Q8W compared to Q4W administrations would be limited and include overly burdensome visit requirements for those randomized to Q8W administration. Additionally, the perceived value for participants to transition from the ATLAS study to ATLAS-2M for potential randomization to the Q8W regimen would also be limited and may result in loss of patients with prior Q4W experience, thereby limiting the ability to compare experience of Q4W and Q8W regimens within individual patients.

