- r. One blood sample for CAB and RPV each to be collected at each PK timepoint. At Day 1, for participant from the ATLAS Q4W arm, PK samples are to be collected pre-dose relative to IM administration. injection. At Week 4b, for participants randomized from SOC, Pre dose PK samples are to be collected: AFTER review of the PK diary to ensure that the samples are taken 20/28 hours after previous oral dose (diaries to be given at Day 1 or W4a); PRIOR to the final oral dose of CAB + RPV; and PRIOR to the first IM injection. At Week 9 and 41, the PK samples should be collected 3 to 10 days after the Week 8 and Week 40 visits, respectively.
- s. Only for Participants entering CAB + RPV Oral Treatment
- t. Participants switching to CAB LA + RPV LA will take final dose of oral lead-in regimen in the clinic at the Week 4b visit and begin injections. If possible, injections should be spaced approximately 2 cm from one another and from the site of any previous injection and or any injection site reaction. Bring RPV LA to approximately room temperature prior to injecting. Time and location of injection (right or left) as well as needle length used will be collected in the eCRF. The first injection can be performed as soon as central lab results become available and safety parameters are reviewed.
- u. All Patient Report Questionnaires/Surveys will be administered via paper instrument at the beginning of the visit before any other assessments are conducted and prior to administration of the eC-CSSRS. Conduct questionnaires/surveys upon Withdrawal only if occurring at or prior to Week 48
- v. The HIVTSQc is to be administered to all participants transitioning from ATLAS and new participants transitioning from oral SOC. For participants transitioning from ATLAS, the version of the HIV-TSQc instrument to be administered will be based on the initial randomization arm at ATLAS Day 1

- w. For patients randomized to oral SOC at Day 1 in ATLAS or new patients on SOC, the reasons for willingness to switch ART will be assessed at Day 1. For patients randomized to CAB LA + RPV LA Q4W in ATLAS, the reasons for willingness to continue long-acting ART in ATLAS-2M will be assessed at Day 1.
- x. Preference Questionnaire will be administered to all participants

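### For participants entering on ATLAS Q4W injections, the PIN endpoint (change from Week 8) subtracts a score taken after the arms have diverged, so it removes whatever Q8W–Q4W difference exists by then

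*Protocol*

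**What the plan says.** Section 3 lists injection tolerability within a secondary objective and defines the PIN dimension and item endpoint as "Change from Week 8 in Dimension scores" and item scores, with the PIN given at Weeks 8, 24 and 48 or Withdrawal. Sections 1.2 and 7.8.1 use the same reference visit. HRQoL, HIVTSQs and ACCEPT are instead measured from Day 1. No Day 1 PIN is named.

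Footnote u of the Time and Events tables places the questionnaires "at the beginning of the visit before any other assessments are conducted". Section 7.8 recommends the same order.

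Dosing before Week 8 depends on route of entry (Section 4.2.2; volumes also in Table 7 of Section 6.3):

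- **From oral SOC, Q4W arm:** "Week 4b visit only - CAB LA 600 mg + RPV LA 900 mg, each given as 1 X 3 mL IM injection". The Q8W arm receives the same dose and volume at Week 4b.
- **From ATLAS Q4W, Q4W arm:** "Starting at Day 1, all injections will continue with maintenance doses of CAB LA 400 mg and RPV LA 600 mg", every 4 weeks. Table 7 gives 2 mL per injection.
- **From ATLAS Q4W, Q8W arm:** "Day 1- CAB LA 600 mg + RPV LA 900 mg IM, each given as 1 X 3 mL IM injection". Then: "Subjects will not require an intermediate dose at Week 4 and will receive their next Q8W maintenance injections at Week 8".

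Section 7.8.1 also has a PIN endpoint that subtracts nothing: the proportion rating pain and local reactions as very or extremely acceptable over time. Section 9.3.7 leaves the remaining health-outcomes analyses to the reporting and analysis plan.

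**The concern.** A change score compares arms fairly only if its reference value is untouched by the difference between the arms. Week 8 meets that condition for one route of entry and not for the other.

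The Protocol intends the tolerability of the two regimens to be compared. Section 2.2 says injection tolerability will be assessed for both. Section 4.4 defends the open-label design partly because it allows tolerability to be compared between Q8W and Q4W, and states that "the volume of CAB LA and RPV LA injections will differ significantly between Q8W and Q4W IM injections". It also values ATLAS Q4W participants because they can compare the two regimens in their own experience. For exactly those participants, the PIN change score starts after the switch. If a difference appears with the first injections of the new volume and interval, the change score understates it, and always towards no difference.

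**Working it through.** The plan states no figure to reproduce, so the check uses the dosing schedule and simple algebra.

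**1. Injections behind each PIN score** (questionnaire completed before that visit's injections, nominal visit weeks, volume per drug):

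| Entry group | Arm | Before Week 8 PIN | Last before Week 24 PIN | Last before Week 48 PIN |
|---|---|---|---|---|
| Oral SOC | Q4W | Week 4b, 3 mL | Week 20, 2 mL | Week 44, 2 mL |
| Oral SOC | Q8W | Week 4b, 3 mL | Week 16, 3 mL | Week 40, 3 mL |
| ATLAS Q4W | Q4W | Day 1 and Week 4, 2 mL | Week 20, 2 mL | Week 44, 2 mL |
| ATLAS Q4W | Q8W | Day 1, 3 mL | Week 16, 3 mL | Week 40, 3 mL |

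In SOC entrants the arms match at Week 8 and differ later. In ATLAS Q4W entrants they already differ at Week 8 in volume and frequency, as they do at Weeks 24 and 48.

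**2. What the change score keeps.** Let d be the true Q8W–Q4W difference in a PIN score at Week 24 or 48, and s the share of d present at Week 8.

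- Expected between-arm difference in change = d − s·d = (1−s)d.
- SOC entrants: s is about 0, so about d is kept.
- ATLAS Q4W entrants: 75% of d is kept at s = 0.25, 50% at 0.5, 25% at 0.75 and 0% at 1.

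**3. Illustration in ATLAS Q4W entrants.** Assumed, not from the documents: 200 per arm, d = 0.3 SD, correlation 0.5 between visits.

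- The variance of a change is 2(1−0.5) = 1, the same as for a level, so both standard errors are √(2/200) = 0.10 SD.
- Level comparison: 0.3/0.10 = 3, power Φ(3−1.96), about 85%, whatever s is.
- Change from Week 8, s = 0.5: 0.15/0.10 = 1.5, power Φ(1.5−1.96), about 32%.
- Change from Week 8, s = 1: expected difference 0, rejection rate 5%.

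A simulation of 4,000 runs gave 85–86% for levels, and 32% and 5% for change at s = 0.5 and s = 1.

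**4. If the entry groups were simply pooled.** With p the proportion of ATLAS Q4W entrants and the same d in both groups, the share kept is 1 − p·s. The documents do not give p. Assuming 30% to 60%:

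- s = 0.5: 1 − 0.15 = 85%, down to 1 − 0.30 = 70%.
- s = 1: 1 − 0.30 = 70%, down to 1 − 0.60 = 40%.

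**5. Week 8 as a covariate instead.** With equal variances the regression slope equals the correlation, so adjustment in ATLAS Q4W entrants would remove 0.5·s·d in this illustration. That is smaller than subtraction removes, but of the same kind.

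**The case against.** The strongest reply is that the Protocol does not fix this endpoint as a Q8W–Q4W contrast. The objective names no comparator, no between-arm PIN test is planned, and the detail is left to the analysis plan. Week 8 also has a reason: SOC entrants have had no study injections at Day 1, so Week 8 is the first PIN visit common to everyone. Other data would sit beside the change score: the acceptability proportion, the HIVTSQs item on painful injectables (analysed from Day 1), graded injection-site reactions, and stated preference.

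Most of this stands, and it limits the weight of the point. It does not remove it. The reference visit is fixed in the Protocol itself, and Sections 2.2 and 4.4 show that the regimens are meant to be compared. The acceptability proportion leaves out leg movement, sleep, anxiety and willingness to be injected. An analysis plan can add level comparisons but cannot recover a Day 1 PIN that was never collected.

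Three stronger readings are tempting, and the documents do not support them:

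- A reader might infer that the endpoint erases the regimen difference. That needs s = 1. It is plausible for acute items, since Section 2.3.1 gives a median injection-site-reaction duration under one week, but s is nowhere quantified and differences that build later survive.
- A reader might infer a known loss across the whole trial. The Protocol does not say the entry groups are pooled for PIN, and p is an assumption.
- A reader might infer that part of the change is recall length, because the last injection is 8 weeks back on Q8W and 4 on Q4W. No PIN recall period is stated, and comparing levels leaves that gap in place.

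In the text available for this review, the PIN row of the Time and Events tables could not be read. The PIN visits are taken from Sections 1.2, 3 and 7.8.1.

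**Conclusion.** The point holds for ATLAS Q4W entrants and for the change-score endpoint only. For them Week 8 is a post-randomisation score on the assigned regimen, and subtracting it leaves (1−s)d. In SOC entrants Week 8 is a sound common reference. The same endpoint therefore measures different things in the two groups.

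The loss runs from none (s = 0) to complete (s = 1), and the documents do not locate it in that range. The conclusion rests on the dosing schedule and on the PIN being completed before that visit's injections. Completion afterwards would not help: ATLAS Q4W entrants would still have diverged, and SOC entrants would by then have had 2 mL and 3 mL Week 8 injections in the two arms.

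A reader might also infer that the endpoint invites a claim of equal tolerability. No such claim is planned. This is a secondary patient-reported endpoint with no formal test, and the primary and key secondary analyses are untouched. It is a cheap improvement worth making.

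**What to change.** 1. In Sections 1.2, 3 and 7.8.1, state that any between-arm PIN comparison uses the dimension and item scores at Weeks 24 and 48 by randomised arm, shown separately for SOC entrants and ATLAS Q4W entrants.
2. In ATLAS Q4W entrants, report Week 8 descriptively. Do not subtract it or adjust for it.
3. In SOC entrants, Week 8 may stay as the reference for change or as a covariate.
4. Optional: add a Day 1 PIN, completed before the first ATLAS-2M injection, for ATLAS Q4W participants still to be enrolled. It would be a true pre-randomisation baseline, collected at a visit that already includes questionnaires.

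The main change uses data already planned and costs wording and a few extra tables. Its downside is some loss of precision in ATLAS Q4W entrants without a Day 1 score. Under the assumptions of the illustration, adjusting for Day 1 would give a standard error of √(2×0.75/200) = 0.087 SD, against 0.10 SD for the unadjusted level comparison.
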